5.10 PACKAGING AND LABELING OF INVESTIGATIONAL DEVICE

See below Figure 3 for example CELLECTRA[™] 5PSP device component labels.

Figure 3. Device Labels (Base, Handset, Array)

ARRAY

5.11 HANDLING OF INVESTIGATIONAL DEVICE

The CELLECTRA[™] 5PSP device and its components must be stored in a secure location according to the instructions in the User Manual.

5.12 INVESTIGATIONAL DEVICE ACCOUNTABILITY

The investigative site is responsible for maintaining investigational device and accountability logs. The device must have full traceability from the receipt of the products through the subject use, disposal or return of the products. The Site must document acknowledgement of receipt and notify Inovio upon receipt of investigational product. This includes the content shipped and condition upon receipt.

For each subject treatment, there must be a record of each product used for that subject, i.e. CELLECTRA[™] 5PSP serial number, array lot number and the study drug lot number. The used sterile disposable array attachment must be discarded after use in accordance with institutional policy regarding disposal of sharp needles/instruments.

5.13 RETURN OF INVESTIGATIONAL DEVICES

Upon completion or termination of the study, all investigational devices and unused components must be returned to Inovio Pharmaceuticals, Inc.

All product returned to Inovio Pharmaceuticals, Inc. must be accompanied by the appropriate return documentation. Returned supplies should be in the original containers. The return of all product identified above should be arranged by the responsible Study Monitor.

If product is to be destroyed on site, it is the Investigator's responsibility to ensure that arrangements have been made for the disposal, written authorization has been granted by Inovio Pharmaceuticals, Inc., or its designee, procedures for proper disposal have been established according to applicable regulation and guidelines and institutional procedures, and appropriate records of the disposal have been documented.

6 STUDY PROCEDURES AND TREATMENTS

This section lists the procedures and parameters for each planned study evaluation. The timing of each assessment is listed in the Schedule of Events Table (see Table 1).

A subject will be required to provide informed consent for use of any information collected prior to consenting and before any additional study specific procedures are performed.

Protocol waivers or exemptions are not allowed with the exception of immediate safety concerns. Therefore, adherence to the study design requirements, including those specified in the Schedule of Events Table are essential and required for study conduct

6.1 BEFORE TREATMENT PROCEDURES

6.1.1 SCREENING EVALUATIONS

After providing informed consent, subject's cervical biopsy tissue samples (e.g., formalin fixed tissue, paraffin-embedded tissue) and/or biopsy slides will be sent to the PAC for review by two study pathologists. Discordant results will be reviewed by a third pathologist to achieve a consensus diagnosis. Subjects must have a diagnosis of histologic HSIL (CIN2 or CIN3) confirmed by the PAC and a screening cervical specimen (i.e. ThinPrep™) test positive for HPV-16 and/or HPV-18 by Cobas™ HPV test to be eligible for randomization into the study (provided the subject also meets other eligibility criteria). Subjects whose specimens also test positive for other HPV genotypes are not excluded as long as they have a positive result for HPV-16 and/or HPV-18. There will be a maximum allowable window of 10 weeks from the date of collection of the qualifying biopsy sample(s) (i.e. slides/samples(s) reviewed by PAC with HSIL consensus diagnosis), until the date of first study treatment (i.e. Day 0).

- Biopsy specimens and colposcopic photographs obtained within 10 weeks prior to Day 0 as part of standard of care before the informed consent may be used as part of the screening and evaluation process.
- If the pathology results of the initial biopsy obtained as part of standard of care are available confirming the presence of HSIL (CIN2 or CIN3), those biopsy slides or sample(s) may be sent directly to the PAC for concurrence after the subject has signed the informed consent.
- For those individuals diagnosed with cervical HSIL by a local pathologist, where the initial biopsy slides or tissue obtained as part of standard of care are not available or cannot be obtained within a reasonable timeframe, colposcopy with cervical photography may be performed and an additional biopsy sample may be collected during screening at the discretion of the investigator and consent of the subject. The additional biopsy sample may be sent directly to the PAC for review, if allowable per local or institutional guidelines.

The assessments during the screening period will determine the subjects' continued eligibility for the study and also their ability to comply with protocol requirements by completing all assessments.

The following evaluations/actions, unless noted, will be performed within 10 weeks and up to 1 day prior to dosing on Day 0 – except for the safety laboratory collections/assessments, which must be performed within 30 days prior to Day 0. All screening assessment values must be reviewed prior to study treatment.

- Signed informed consent
- ThinPrep[™] sample for HPV typing and pap smear (subject should be requested to abstain from sexual activity and refrain from use of douching or vaginal lubricants/medication for a period of 24 hours prior to sample collection)
- Colposcopy with lesion photography and cervical biopsy
- Demographics; including age, and race/ethnicity
- Medical history; including concomitant medications review, history of prior cervical dysplasia, and pregnancy history

- Socio-Behavioral Assessment; including self-reported smoking history, self-reported exposure to second-hand smoke, self-reported alcohol intake history, contraceptive history
- Determination of eligibility per inclusion / exclusion criteria
- Full Physical Examination (including height, weight and BMI measurements)
- Vital signs (including oral temperature, respiratory rate, blood pressure and heart rate)
- 12-lead ECG (within 30 days prior to Day 0)
- Baseline laboratory evaluations (includes CPK, hematology and serum chemistry, urinalysis) to be performed (within 30 days prior to Day 0);
- Urine pregnancy test
- Serology (HIV Antibody) (within 30 days prior to Day 0)
- Whole blood (at least 34 mL) and serum (at least 4 mL) for baseline immunologic assay
- 2 Digene cervical brush samples

6.2 DURING TREATMENT PROCEDURES BY VISIT

Once eligibility has been confirmed, the subject will be randomized to receive study treatment. Visit dates and windows must be calculated from Day 0.

6.2.1 DAY 0

The following evaluation will be performed on **Day 0 prior to study treatment:**

- Determination of eligibility per inclusion / exclusion criteria
- Randomization
- Targeted Physical Exam
- Vital signs
- Urine pregnancy test
- Whole blood (at least 34 mL) and serum (at least 4 mL) for baseline immunologic assay (a total of at least 68 mL of whole blood and 8 ml serum should be collected prior to dosing on Day 0)
- Colposcopy with lesion photography
- ThinPrep[™] sample for HPV typing and pap smear (subject should be requested to abstain from sexual activity and refrain from use of douching or vaginal lubricants/medication for a period of 24 hours prior to sample collection)
- 2 Digene cervical brush samples
- Oropharynx (OP) sample by oral rinse and vaginal and anal swabs
- Patient-Reported Outcomes (PROs) completion

Study treatment will be administered and the following evaluations will be performed on **Day 0** post-treatment:

- Post treatment adverse event and injection site reaction assessment within a minimum of 30 minutes after study treatment
- Distribute Participant Diary Card (PDC)

• Download EP data from device

6.2.2 8-14 DAYS POST DOSE 1 PHONE CALL

The following information will be evaluated during phone call:

- Post treatment adverse event and injection site reaction evaluation
- Review Day 0 PDC
 - The subject should submit their PDC (via email, fax, mail) to site personnel prior to the phone visit. If the PDC is not received in advance, site personnel should review all diary elements verbally. The hard copy of the PDC should be collected and reviewed at the next in-person study visit. After completing a review of PDC and post treatment injection assessment with the subject on the phone, the Investigator or study personnel will determine whether an office visit is needed for further evaluation.
- PRO completion

6.2.3 WEEK 4

The following study evaluation will be performed on Week 4 prior to study treatment (± 4 days):

- Targeted Physical Exam
- Vital signs
- Urine pregnancy test
- Collect PDC for dose 1

The following study evaluations will be performed on Week 4 post treatment:

- Post treatment adverse event and injection site reaction assessment within a minimal of 30 minutes after study treatment;
- Distribute PDC
- Download EP data from device

6.2.4 8-14 DAYS POST DOSE 2 PHONE CALL

The following information will be evaluated during phonecall:

- Post treatment adverse event and injection site reaction evaluation
- Review PDC for dose 2
 - O The subject should submit their PDC (via email, fax, mail) to site personnel prior to the phone visit. If the PDC is not received in advance, site personnel should review all diary elements verbally. The hard copy of the PDC should be collected and reviewed at the next in-person study visit. After completing a review of PDC and post treatment injection assessment with the subject on the phone, the Investigator or study personnel will determine whether an office visit is needed for further evaluation.
- PRO completion

6.2.5 WEEK 12

The following study evaluation will be performed on Week 12 prior to study treatment (± 4 days):

- Targeted Physical Exam
- Vital signs
- Urine pregnancy test
- Collect PDC regarding Dose 2

The following study evaluations will be performed Week 12 post treatment:

- Post treatment adverse event and injection site reaction assessment within a minimal of 30 minutes after study treatment;
- Distribute PDC
- Download EP data from device

6.2.6 8-14 DAYS POST DOSE 3 PHONE CALL

The following information will be evaluated during phonecall:

- Post treatment adverse event and injection site reaction evaluation
- Review PDC for dose 3
 - The subject should submit their PDC (via email, fax, mail) to site personnel prior to the phone visit. If the PDC is not received in advance, site personnel should review all diary elements verbally. The hard copy of the PDC should be collected and reviewed at the next in-person study visit. After completing a review of PDC and post treatment injection assessment with the subject on the phone, the Investigator or study personnel will determine whether an office visit is needed for further evaluation.
- PRO completion

6.2.7 WEEK 15

The following study evaluations will be performed on Week 15 \pm 1 week:

- Targeted physical assessment
- Vital signs
- Urine pregnancy test
- Whole blood (at least 51 mL) and serum (at least 4 mL) for immunologic assays
- Post-treatment injection site reaction assessment
- ThinPrep[™] sample for HPV typing and pap smear (subject should be requested to abstain from sexual activity and refrain from use of douching or vaginal lubricants/medication for a period of 24 hours prior to sample collection)
- 2 Digene cervical brush samples
- Oropharynx (OP) by oral rinse and vaginal and anal swabs

- Collect PDC
- Colposcopy and lesion photography

6.2.8 WEEK 28

The following study evaluations/actions will be performed on Week 28 ± 1 weeks:

- Targeted physical Assessment
- Vital signs
- Urine pregnancy testing
- ThinPrep[™] sample for HPV typing and pap smear (subject should be requested to abstain from sexual activity and refrain from use of douching or vaginal lubricants/medication for a period of 24 hours prior to sample collection)
- 2 Digene cervical brush samples
- Colposcopy and lesion photography to assess for possible disease progression
- PRO to be completed by subject 8-14 days after Week 28 visit

6.2.9 WEEK 36

The following study evaluations will be performed on Week 36 ± 1 week:

- Socio-Behavioral Assessment; including self-reported smoking history, self-reported exposure to second-hand smoke, self-reported alcohol intake history, contraceptive history
- Targeted physical assessment
- Vital signs
- Whole blood (at least 34 mL) and serum (at least 4 mL) for immunologic assays
- Urine pregnancy test
- ThinPrepTM sample for HPV typing and pap smear (subject should be requested to abstain from sexual activity and refrain from use of douching or vaginal lubricants/medication for a period of 24 hours prior to sample collection)
- 2 Digene cervical brush samples
- Oropharynx (OP) by oral rinse and vaginal and anal swabs
- Colposcopy and lesion photography
- Biopsy or surgical excision

The investigator will utilize information collected at Week 28 to determine the appropriate method for obtaining tissue for histopathologic assessment as described in Tables 4 & 5 for minimally required procedure (4 quadrant biopsies, 4 quadrant biopsies and ECC, or excision).

6.2.10 WEEK 40 PHONE CALL

The following study evaluations will be performed on Week 40 ± 2 weeks via a phone call:

- Review of histology results as read by PAC from Week 36
- PRO to be completed by subject 8-14 days after Week 40

6.2.11 WEEK 62

The following study evaluations will be performed on Week 62 ± 2 weeks:

- Targeted physical assessment
- Vital Signs
- ThinPrep[™] sample for HPV typing and pap smear (subject should be requested to abstain from sexual activity and refrain from use of douching or vaginal lubricants/medication for a period of 24 hours prior to sample collection)
- 2 Digene cervical brush samples
- Colposcopy and lesion photography

6.2.12 WEEK 88

The following study evaluations will be performed on Week 88 ± 2 weeks:

- Socio-Behavioral Assessment; including self-reported smoking history, self-reported exposure to second-hand smoke, self-reported alcohol intake history, contraceptive history
- Full Physical Exam
- Vital Signs
- ThinPrep[™] sample for HPV PCR and pap smear (subject should be requested to abstain from sexual activity and refrain from use of douching or vaginal lubricants/medication for a period of 24 hours prior to sample collection)
- 2 Digene cervical brush samples
- Colposcopy and lesion photography
- Whole blood (at least 34 mL) and serum (at least 4 mL) for immunologic assays
- Oropharynx (OP) by oral rinse and vaginal and anal swabs
- PRO completion

6.3 EVALUATIONS AND PROCEDURES

6.3.1 INFORMED CONSENT

All subjects must sign the informed consent prior to any study related procedures being performed (i.e., prior to any screening activities). The informed consent documentation must be in accordance with applicable regulations and GCP. Qualified study personnel will meet with prospective study subjects, explain the study, and provide them with an informed consent form (ICF) that describes the screening tests, eligibility criteria for entering the study, study treatments and follow-up procedures, in a language understandable to the subject. Explanation of the study includes, but is not limited to, study objectives, potential benefits and risks, discomforts/inconveniences, and the subject's rights and responsibilities. The subject is then requested to sign and date the ICF. A copy of the signed informed consent documentation must be provided to the subject. The qualified study personnel will document the process of obtaining informed consent within the source record. Signed ICFs are maintained in the subject's source records and must be accessible for verification at any time.

6.3.2 ASSIGNMENT OF SUBJECT IDENTIFICATION NUMBERS

Each subject who consents will be assigned a unique subject identification number (SID), which identifies the subject for all study-related procedures. SIDs are a combination of a up to two alpha letters study code, two alpha letter Country code, two digit site number, plus 3-digit subject number starting with (e.g., Country code, SIDs cannot be reused for any reason. Information regarding the SID and screen date must be documented on a Screening log/system and in the Interactive Response Technology (IXRS).

Subjects meeting eligibility criteria will be randomized by a computer generated allocation schedule.

6.3.3 SAFETY EVALUATIONS

6.3.3.1 Physical Exam

A full physical examination (PE) will be conducted during screening and study discharge. It will include an assessment of the following: general appearance, skin, head, eyes, ears, nose, and throat, and lymph nodes, and respiratory, cardiovascular, gastrointestinal, genitourinary, musculoskeletal, and neurological systems.

A targeted physical assessment will be performed at other visits as determined by the investigator or directed per subject complaints. The injection site is to be assessed by the study personnel at 30 minutes after each study treatment.

6.3.3.2 Vital Signs

Vital signs will be measured at specified visits and will include:

- Sitting systolic and diastolic blood pressures with subject sitting at rest for at least 5 minutes before measurement
- Respiration rate
- · Heart rate
- · Oral temperature measured with an automated thermometer

6.3.3.3 Weight and Height

Weight (kg) and height (cm) will be collected at screening in order to calculate the BMI $(BMI = kg/m^2)$.

6.3.3.4 Medical History

All relevant (as judged by the investigator) past and present conditions at screening, as well as prior surgical procedures will be recorded for the main body systems. The medical history will include a) any prior history of CIN diagnosed – with diagnosis date(s) and respective CIN level(s), and b) if treated previously for CIN, the respective treatment type(s) and date(s).

6.3.3.5 Socio-Behavioral Assessment

Socio-Behavioral Assessment, including self-reported smoking history, self-reported history of exposure to second-hand smoke, self-reported alcohol intake history, self-reported recreational drug use history, self-reported history of contraceptive use and type of contraceptive if known, reproductive history, history of prior cervical dysplasia, and pregnancy history will be obtained.

6.3.3.6 Laboratory Evaluations

At screening, blood samples will be taken to be tested for serum chemistry and hematology.

Complete blood count (CBC):

- White blood cell (WBC) count w/ differential
- Red blood cell (RBC) count
- Hemoglobin, Hematocrit
- Platelet count

Serum Chemistry:

- Glucose
- SGPT (serum glutamic-pyruvic transaminase)/ALT
- BUN (blood urea nitrogen)
- Creatinine
- Electrolytes (Sodium, Potassium, Chloride, Carbon Dioxide or Bicarbonate)
- CPK (creatine phosphokinase)

Urinalysis (UA):

Urine samples will be tested at screening by dipstick for glucose, protein, and hematuria. If abnormal (presence of protein, hematuria, or glucose $\geq 1+$) a microscopic examination should be performed.

6.3.3.7 Demographics

Demographic information will be collected via self-report (unless noted otherwise), including the following:

- Age (via date of birth)
- Race/ethnicity

6.3.3.8 Urine Pregnancy Testing

For subjects of reproductive potential, a negative spot urine pregnancy test is required prior to each study treatment, colposcopy and surgical excision.

6.3.3.9 ECG

A single 12-lead ECG will be obtained during Screening after the subject has been in a supine position for 10 to 15 minutes. The ECG should include measurements of ventricular rate, PR, QRS, QRS axis, QT, QTcb or QTcf, ST segment, Twave as well as an investigator

assessment of whether the ECG is normal or abnormal (automated interpretations of ECG should not be used). Abnormal ECGs should be interpreted as "clinically significant (CS)" or "not clinically significant (NCS)" by the investigator

6.3.3.10 Subject Post Treatment Assessments

PDC will capture subject reported local and systemic events for 7 days after the study treatment as shown in Appendix A.

The subject will be provided a PDC and will be asked to record the following the evening of study treatment through Day 6:

- Oral temperature and time taken (before 11:59 pm)
- General symptoms of feeling unwell
- Pain and itching at injection site
- Measure redness, swelling, bruising at injection site
- Medications taken

The completed PDC will be reviewed with the subject and research staff at 8 -14 Days post-dose.

The study staff will review the PDC for general symptoms (e.g. malaise, fatigue, headache, nausea, and myalgia/arthralgia), injection site reaction symptoms (e.g. pain, erythema and edema), medical events and medications. All reported events will be assessed for clinical significance (CS) and reported as adverse event accordingly.

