7 EVALUATION OF SAFETY AND MANAGEMENT OF TOXICITY

7.1 SAFETY PARAMETERS

7.1.1 ADVERSE EVENTS

An adverse event (AE) is defined as any unfavorable and unintended change in the structure, function, or chemistry of the body, or worsening of a pre-existing condition, temporally associated with the use of a product whether or not considered related to the use of the product. In this study, such changes will be monitored, classified, and summarized, as Clinical or Laboratory AEs. Medical condition/diseases present before starting the investigational drug will be considered adverse events only if they worsen after starting study treatment. Throughout the course of the study, all solicited and unsolicited AEs will be monitored and reported on an AE CRF, including the event's seriousness, severity, action taken, and relationship to investigational product(s). AEs should be followed until resolution or stable and the outcome will be documented on the appropriate CRF. All AEs should be recorded in standard medical terminology rather than the subject's own words.

AEs include the following:

• Pre- or post-treatment complications that occur as a result of protocol mandated procedure during or after screening (before the administration of study drug).

- Any pre-existing condition that increases in severity, or changes in nature during or as a consequence of the study drug phase of a human clinical trial, will also be considered an AE.
- Complications of pregnancy; see Section 7.1.9 for additional information.
- AEs that occur from the study screening visit onwards and throughout the duration of the study, including the follow-up off study drug period will be recorded as an AE.
- Conditions that lead to a medical or surgical procedure.

AEs do not include the following:

- Medical or surgical procedures (e.g., surgery, endoscopy, tooth extraction, transfusion) performed as a result of an AE.
- Pre-existing diseases or conditions or laboratory abnormalities present or detected before the screening visit that do not worsen.
- Situations where an untoward medical occurrence has not occurred (e.g., hospitalization for elective surgery, social and/or convenience admissions).
- Overdose without clinical sequelae.
- Any medical condition or clinically significant laboratory abnormality with an onset date before the informed consent form is signed is not an AE. It is considered to be pre-existing and will be documented on the medical history CRF.

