8.11 SAFETY ANALYSES

8.11.1 ADVERSE EVENTS

All AEs will be summarized among the safety population by frequency per treatment arm. These frequencies will be presented overall and separately by dose, and will depict overall, by system organ class and by preferred term, the percentage of subjects affected. Additional frequencies will be presented with respect to maximum severity and to strongest relationship to Study Treatment. Multiple occurrences of the same AE will be counted only once following a worst-case approach

with respect to severity and relationship to Study Treatment. All serious AEs will also be summarized as above.

The main summary of safety data will be based on events occurring within 14 days of any dose. For this summary, the frequency of preferred term events will be compared between study arms with risk differences and 95% confidence intervals, using the method of Miettinen and Nurminen [27]. As this analysis will use many event categories, and produce many confidence intervals, caution should be exercised when interpreting these confidence intervals. Separate summaries will be based on events occurring within 7 days of any dose and regardless of when they occurred.

Any AEs with a missing or partial onset date will be included in the overall AEs, but not be included within specified day-range summaries. AE duration will be calculated as (Stop Date – Start Date) + 1.

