9.5.1 STUDY REPORTING PERIOD OF ADVERSE EVENTS

All solicited and unsolicited adverse events will be collected throughout the study and recorded on the AE CRF. Safety events will be analyzed and summarized throughout the study. Emphasis will be placed on the following:

- Certain AEs of interest will be solicited during the 7 days following each administration of Study Treatment and summarized separately
- Unsolicited AEs, SAEs or UADEs will be collected and summarized for the entire study period

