3.3 SECONDARY OBJECTIVES AND ASSOCIATED ENDPOINTS

Secondary Objectives	Associated Secondary Endpoints
	1a. Incidence and severity of local and systemic
VGX-3100 delivered IM followed by EP	events for 7 and 28 days following each
with CELLECTRA [™] 5PSP	investigational treatment and for the duration
	of the study (through Week 88 visit)
	1b. Incidence and severity of SAE and UADE for 7
	and 28 days following each investigational
	treatment and for the duration of the study
	(through Week 88 visit)
2.Determine VGX-3100 efficacy compared	2
to placebo as measured by histopathologic	cervical HSIL on histology (i.e. biopsies or
regression of cervical HSIL	excisional treatment) at Week 36 visit
3.Determine VGX-3100 efficacy compared	3. Proportion of subjects with no evidence of HPV-
to placebo as measured by virologic	16 and/or HPV-18 in cervical samples by type
clearance of HPV-16 and/or HPV-18	specific HPV testing at Week 36 visit
4.Determine VGX-3100 efficacy compared	
to placebo as measured by complete	grade squamous intraepithelial lesion (LSIL) or
histopathologic regression of cervical	,
HSIL to normal	on histology (i.e. biopsies or excisional
	treatment) at Week 36 visit
5.Determine VGX-3100 efficacy compared	1
to placebo as measured by both complete	or HSIL (i.e. no evidence of CIN1, CIN2 or
histopathologic regression of cervical	CIN3 on biopsies or excisional treatment) on
HSIL to normal and virologic clearance of	histology (i.e. biopsies or excisional treatment)
HPV-16 and/or HPV-18	and no evidence of HPV-16 and/or HPV-18 by
	type specific HPV testing at Week 36 visit
6.Determine the efficacy of VGX-3100	
compared with placebo as measured by	cervical HSIL to cervical carcinoma from
histopathologic non-progression	baseline on histology (i.e. biopsies or excisional
	treatment) at Week 36 visit
7.Describe the clearance of HPV-16 and/or	
HPV-18 infection from non-cervical	and/or HPV-18 on specimens from non-cervical
anatomic locations	anatomic locations (i oropharynx, vagina and
	intra-anal) at Week 36 Visit
	8a. Levels of serum anti-HPV-16 and anti-HPV-18
immune response following administration	antibody concentrations at baseline, Week 15,
of VGX-3100 compared with placebo at	36, and 88 visits
	8b. Interferon-γ ELISpot response magnitudes at
compared to baseline	baseline, Weeks 15, 36, and 88 visits
	8c. Flow Cytometry response magnitudes at
	baseline and Week 15 visits

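### Section 6.3.3.10 applies a clinical-significance step to diary events that 6.6, 7.1.1, 7.2 and 9.5.1 do not have, so mild solicited reactions may be under-recorded as AEs and endpoint 1a may be understated

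*Protocol*

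**What the plan says.** Section references are to protocol v2.1 unless stated.

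- **Diary (6.3.3.10).** "PDC will capture subject reported local and systemic events for 7 days after the study treatment as shown in Appendix A". The card in Appendix A asks each day about five general symptoms, about pain and itching at the injection site, and about redness, swelling and bruising, from the evening of treatment through Day 6. Staff then review it: "All reported events will be assessed for clinical significance (CS) and reported as adverse event accordingly".
- **AE definition and recording (7.1.1).** An AE is "any unfavorable and unintended change in the structure, function, or chemistry of the body", or worsening of an existing condition, in temporal association with the product. Throughout the study, "all solicited and unsolicited AEs will be monitored and reported on an AE CRF".
- **Reporting period (9.5.1).** "All solicited and unsolicited adverse events will be collected throughout the study and recorded on the AE CRF". It adds: "Certain AEs of interest will be solicited during the 7 days following each administration of Study Treatment and summarized separately".
- **Endpoint 1a (3.3).** "Incidence and severity of local and systemic" events over 7 and 28 days after each treatment and over the whole study. Protocol v3.0 keeps this endpoint.
- **Analysis (8.11.1).** "All AEs will be summarized among the safety population by frequency per treatment arm". The same section provides the separate 7-day summary.

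**The concern.** The diary is meant to capture what women experience after each injection and electroporation. If an entry must also be judged clinically significant before it becomes an AE, the recorded rate depends on the assessor's threshold as well as on the reaction. The entries most exposed are mild ones, which Table 12 grades as 1: pain that leaves activity unaffected, or erythema of 2.5-5 cm. One site could follow 6.3.3.10 and leave such an entry out, while another follows 7.1.1 and 9.5.1 and records it. The protocol plans for about 100 sites (v2.1) or 125 (v3.0) in up to 25 countries, so there is room for thresholds to differ.

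The tolerability result is at stake: how often solicited reactions occur, at what grade, and how the arms compare. Section 2.3 describes the Phase 2b administration-site reactions as generally mild. Primary efficacy is not touched.

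**Working it through.** The plan states no figure on this point, so the check is to set the sections side by side.

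1. **What 6.3.3.10 does.** It has diary events assessed for significance and reported as AEs accordingly. The section just before it, 6.3.3.9, uses the same abbreviation for a two-way call on abnormal ECGs, significant or not. Read the same way here, a significant entry becomes an AE and any other does not. The text does not define significance for a symptom, say who decides, or say what happens to an entry judged not significant.

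2. **What the other sections do.**
   - 6.6 already calls the diary entries local and systemic AEs.
   - 7.1.1 defines an AE without a significance threshold and sends all solicited AEs to the AE form.
   - 7.2 lists symptoms reported by the subject as an AE source in their own right. Its significance test is attached to evaluations and examinations.
   - 7.1.7 uses investigator-judged significance as one criterion for laboratory abnormalities.
   - 9.5.1 repeats that all solicited AEs are recorded.

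   Outside 6.3.3.10, then, the AE-recording rules confine the significance test to findings and laboratory values.

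3. **How it reaches the endpoint.** The 8.11.1 frequencies, including the 7-day summary, count AEs. If endpoint 1a is taken from those tables, the filter acts on it.

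4. **Direction.** Let D be the number of women with a given reaction in the diary and A the number with the matching AE record. A filter can only remove events, so A ≤ D. If the removed entries are mainly Grade 1, the grade mix among recorded events also shifts upward.

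5. **Size.** No document gives the share of diary entries that would be judged significant, so A/D cannot be computed. As arithmetic only, take the Phase 2b erythema rates in 2.3, 78% and 57%, and assume that a share r of affected women is retained, equal in both arms. Recorded rates are 78r and 57r, and the difference is 21r points.

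| r (assumed) | VGX-3100 | Placebo | Difference (points) |
|---|---|---|---|
| 1 | 78.0% | 57.0% | 21.0 |
| 0.75 | 58.5% | 42.75% | 15.75 |
| 0.5 | 39.0% | 28.5% | 10.5 |
| 0.25 | 19.5% | 14.25% | 5.25 |

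No row is an estimate. The range shows only that the result would depend on a quantity the plan leaves to judgement. If r differed between arms, the difference would not follow this pattern.

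**The case against.** The case on the other side has several parts.

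- **The wording is not literally a filter.** 6.3.3.10 never says that an entry judged not significant is dropped, and the recording sentences in 7.1.1 and 9.5.1 speak of events already classed as AEs. This stands: *only if significant* is the natural reading, not the text. The conflict therefore rests most firmly on the AE definition, on 6.6 and on 7.2. If another reading was meant, sites still lack one clear rule.
- **The endpoint may not come from AE records.** Endpoint 1a speaks of events, 9.5.1 promises a separate summary of solicited events, and a statistical analysis plan that is not shown may tabulate the diary directly. This also stands, as a condition on the bias. The separate summary does not settle it, because 9.5.1 still describes those events as AEs.
- **Other text favours recording mild reactions.** Table 12 has a Grade 1 for use throughout the study, and 7.3 requires administration-site reactions and complaints to be documented. Section 2.3 lists the generally mild Phase 2b reactions among the most common AEs. That weakens any claim that mild events will be lost, but it sharpens the inconsistency with 6.3.3.10.
- **The current text may differ.** v3.0 as shown breaks off in 6.1.1, and its contents list moves AE reporting to section 7.4. Its summary of changes lists nothing for 6.3.3.10, but covers only significant changes, so it does not prove that the sentence survived.

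A reader might infer that reactogenicity will be understated, and by roughly the amounts in the table. The documents do not support that. The retained shares are assumed, and *generally mild* describes administration-site reactions as a group, not erythema in particular. A reader might also take Table 12 as an objective grade for every diary item. It has no row for itching, bruising or the general symptoms, and its pain and tenderness grades are not objective measurements.

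**Conclusion.** The point holds as an inconsistency in a recording rule that feeds a named secondary safety endpoint. Section 6.3.3.10, on its natural reading, sets a condition that 6.6, 7.1.1, 7.2 and 9.5.1 do not. Mild solicited reactions may be under-recorded as AEs, and recorded differently by site. Endpoint 1a may then be understated.

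That last step assumes that the endpoint is tabulated from AE records, as 8.11.1 suggests, and that some diary entries are judged not significant. The direction follows from those assumptions; the size cannot be computed from the documents. The conclusion concerns v2.1 and has to be checked against the v3.0 text of the section. The change should be made because it is cheap and the rule is stated, not because a bias of known size has been shown.

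**What to change.** In 6.3.3.10, remove the clinical-significance step for solicited diary items. State that every solicited event on Days 0-6 is recorded, graded and counted in endpoint 1a whether or not it is thought significant. Grade by Table 12 where it has a row, and otherwise by the CTCAE version named in 7.1.5. Because the lowest erythema and swelling grade in Table 12 starts at 2.5 cm, say how smaller areas are counted; for erythema the table's footnote already asks for the measurement as a continuous variable. Keep the significance judgement for examination and laboratory findings, where 7.2 and 7.1.7 use it. Confirm that 6.3.3.10 and the AE reporting section of v3.0 carry the same rule, and align the CRF completion guideline.

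The cost is a one-sentence edit with its grading note, more mild-event rows for sites to enter, and higher reported reaction rates.
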